10.4.3 Secondary Endpoint(s)

Table 10.4.3-1: Endpoints

Secondary Endpoint	Description	Timeframe
Effect on LVOT gradient	
 Change from baseline to EOT-A in post-exercise LVOT peak gradient Change from baseline to EOT-A in resting LVOT peak gradient, change from baseline to EOT-A in Valsalva LVOT peak gradient Proportion of participants achieving a resting LVOT peak gradient of < 30 mm Hg and a Valsalva LVOT peak gradient < 50 mm Hg at EOT-A 	Up to EOT-A
PK/PD relationship	
Concentration response relationship between MYK-224 and resting, Valsalva, and post-exercise LVOT peak gradients.
 
Concentration response relationship between MYK-224 and echocardiographic parameters of systolic and diastolic function including:
 
 LV ejection fraction (LVEF) LV fractional shortening LVOT velocity time integral LV global longitudinal strain (GLS) LV stroke volume E/A ratio Lateral, septal, and average e' Lateral, septal, and average E/e' 	Up to EOS-A
PK concentrations	Summary of plasma concentrations	Up to EOS-A

Abbreviations: A, late diastolic mitral inflow velocity; E, early diastolic mitral inflow velocity; e', early diastolic mitral annular tissue velocity (note there is a lateral, septal and average of this parameter); E/A, early to late diastolic mitral inflow velocity ratio (or early diastolic mitral inflow velocity to late diastolic mitral inflow velocity ratio); E/e', early diastolic mitral inflow velocity to early diastolic mitral annular tissue velocity ratio (note: there is a lateral, septal and average of this parameter, depending on where the tissue velocity assessment is made lateral or septal [medial annulus]); EOS, end of study; EOT, end of treatment; LV, left ventricular; LVEF, left ventricular ejection fraction; LVOT, left ventricular outflow tract; PD, pharmacodynamic; PK, pharmacokinetics.

All secondary endpoint analyses will be performed on Efficacy/PD population or PK population. All endpoints related to the effect of MYK-224 on LVOT gradient parameters will be listed by participants and summarized by timepoint and subgroup. Ninety percent confidence interval will be presented, if possible. The PK/PD relationship parameters will be explored by graphical and regression analyses. All concentration-time data will be listed and summarized by timepoint and subgroup descriptively.

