1 PROTOCOL SUMMARY

Protocol Title:

A Phase 2a, Open-label, Pilot Study to Evaluate Efficacy, Pharmacokinetics, Pharmacodynamics, Safety, and Tolerability of MYK-224 in Participants with Symptomatic Hypertrophic Cardiomyopathy and Left Ventricular Outflow Tract Obstruction

Brief Title:

Multiple Dose Study to Evaluate Efficacy, Pharmacokinetics, Pharmacodynamics, Safety, and Tolerability of MYK-224 in Participants with Symptomatic Obstructive Hypertrophic Cardiomyopathy

Rationale:

This is a proof-of-mechanism Phase 2a study in participants with obstructive hypertrophic cardiomyopathy (oHCM) to support future studies of MYK-224 (also known as BMS-986435) in this patient population. This study is supported by preclinical Good Laboratory Practices (GLP) toxicity and safety studies, as well as safety and tolerability data from the on-going first-in-human (FIH) study in healthy participants. The aim of this study is to characterize the safety, tolerability, efficacy, pharmacokinetics (PK), and pharmacodynamics (PD) of MYK-224 in participants with oHCM. The current study was designed to generate multiple-dose data in participants using intra-patient dose titration (Part A). The initial titration will be followed by an optional open-label extension (OLE) to [REDACTED] (Part B). The results of this study are expected to facilitate future studies, including dose selection, in patient populations.

Objectives and Endpoints:

Objectives	Endpoints
Primary	

 To assess the safety and tolerability of MYK-224 in participants with symptomatic oHCM (Part A) 	
 AEs and SAEs (incidence, severity, causality), including cardiovascular events and hospitalizations Incidence of arrhythmias, including atrial fibrillation/flutter (new from screening and recurrent), ventricular tachyarrhythmias (ventricular tachycardia, ventricular fibrillation, and Torsades de Pointe) Incidence of appropriate implantable cardioverter defibrillator therapy and resuscitated cardiac arrest Results of vital signs, physical exams, 12-lead ECG (including HR), TTE, clinical laboratory tests (including hematology, clinical chemistry, and urinalysis)
Secondary	

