4 OBJECTIVES AND ENDPOINTS

Table 4-1: Objectives and Endpoints

Objectives	Endpoints
Primary 
 To assess the safety and tolerability of MYK-224 in participants with symptomatic oHCM (Part A) 	Primary 
 AEs and SAEs (incidence, severity, causality), including cardiovascular events and hospitalizations Incidence of arrhythmias, including atrial fibrillation/flutter (new from screening and recurrent), ventricular tachyarrhythmias (ventricular tachycardia, ventricular fibrillation, and Torsades de Pointe) Incidence of appropriate implantable cardioverter defibrillator therapy and resuscitated cardiac arrest Results of vital signs, physical exams, 12-lead ECG (including HR), TTE, clinical laboratory tests (including hematology, clinical chemistry, and urinalysis)
Secondary 
 To evaluate the effect of MYK-224 on LVOT gradient in participants with symptomatic oHCM (Part A) To assess the PK/PD relationship of MYK-224 (Part A) To assess the PK of MYK-224 in participants with symptomatic oHCM (Part A) 	Secondary 
 Relief of obstruction as measured by change in LVOT peak gradient (post-exercise, resting, and Valsalva) from baseline to end of treatment (Part A) Proportion of participants achieving a resting LVOT peak gradient of < 30 mm Hg and a Valsalva LVOT peak gradient < 50 mm Hg at end of treatment (Part A) Concentration-response relationship between MYK-224 PK and 1) LVOT peak gradients; and 2) echocardiographic parameters of systolic and diastolic function Summary of plasma concentrations

Table 4-1: Objectives and Endpoints

Objectives	Endpoints
Exploratory (Part A)	Exploratory (Part A)

Table 4-1: Objectives and Endpoints

Objectives	Endpoints
Exploratory (Part B)	Exploratory (Part B)

Table 4-1: Objectives and Endpoints

Objectives	Endpoints
[REDACTED]	
Abbreviations: [REDACTED] AE, adverse event; [REDACTED]; ECG, electrocardiogram; EOT, end of treatment; EOT-A, end of treatment for Part A; HCM, hypertrophic cardiomyopathy; [REDACTED]; HR, heart rate; [REDACTED]; LVOT, left ventricular outflow tract; [REDACTED]; oHCM, obstructive hypertrophic cardiomyopathy; OSS, overall summary score; PD, pharmacodynamics; PK, pharmacokinetics; SAE, serious adverse event; [REDACTED]; TTE, transthoracic echocardiogram.	

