5.1.1.2 Treatment Period (Part A)

The treatment period is designed to identify the target individual dose for each participant. Dose titration will be based on measures taken at steady state (at least 21 days after dose initiation) and occur approximately every 4 weeks. Once the target individual dose has been identified for each participant, the participant will continue to the Stable Dosing period. The Dose Titration period and Stable Dosing period are described below.

Dose Titration Period

The study will include an intra-patient dose titration scheme designed to achieve safe and effective dosing for each participant by determining a target individual dose guided by their own response parameters. Participants who meet all eligibility criteria at Screening will begin study treatment with MYK-224. Dosing will consist of a once daily (QD) oral dose in the form of tablets. All participants will begin at an initial dose of 5 mg of MYK-224, followed by up- or down-titration to doses between 2.5 mg and 50 mg.

Participants will return to the investigational site for [REDACTED] clinic visits as outlined in [Table 2-2](#) and [Figure 5.1.1-1](#). These visits will include PK sample collection, [REDACTED], [REDACTED], safety laboratory collection, 12-lead ECGs, clinical evaluations (eg, vital signs, clinical outcome assessments [COAs], concomitant medication use), and echocardiography.

Dose titration will be based on TTE measures taken at 3 weeks (at least 21 days) post-initiation of each new dose. Participants will repeat this 4-week period as needed to identify their individual target dose. Details on dose titration can be found in [Section 7.4.1.1](#).

Stable Dosing Period

Once the individual target dose is identified, participants will continue dosing until 2 criteria are met: 1) 6 weeks (at least 42 days) total dosing at their target dose (including the 4-week titration period, if applicable); and 2) an overall minimum total treatment period of 12 weeks (at least 84 days) at any dose or combination of doses. See [Section 7.4.1.2](#) for details regarding dose modification during stable dosing and the impact of any modification on the criteria for study completion. During this period, participants will have [REDACTED] clinic visits to collect PK samples, [REDACTED], 12-lead ECG and TTE measures, and safety assessments (see [Table 2-3](#)). The final dose of MYK-224 will be administered in clinic at an end-of-treatment visit.

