The objective of the study is to evaluate the safety, tolerability, and efficacy of MYK-224 alone and in combination with SOC therapies for HCM. The cohorts are staggered so that data from ongoing studies may be evaluated prior to initiating Cohort 2 to allow for modification of the starting dose or dose titration schedule if necessary. Cohort 2 includes participants with SOC consisting of either a nondihydropyrimidine calcium channel-blocker (verapamil or diltiazem) or dihydropyrimidine in combination with a beta-blocker or nondihydropyrimidine calcium channel-blocker. Both verapamil and diltiazem are moderate inhibitors of CYP3A4.

The initiation of Cohort 2 will be at the discretion of the Sponsor and will be informed by data obtained from Cohort 1, as well as from 2 on-going studies: 1) CV029005, a DDI study evaluating the effect of co-administration of MYK-224 and moderate (verapamil) and strong (itraconazole) [REDACTED] in healthy participants; 2) MYK-461-017 (VALOR-HCM), a clinical study evaluating mavacamten (a similar cardiac myosin inhibitor) in participants with oHCM who are eligible for septal reduction therapy, which includes the [REDACTED]. Cohort 2 will only be initiated once 50% of Cohort 1 participants have reached their target dose and the data from the CV029005 and VALOR-HCM study are available. The same dosing regimen as Cohort 1 will be used for Cohort 2 unless data from Cohort 1 and the indicated studies supports a change to this schedule.

Participants who successfully complete Part A will have the option to continue the study drug as a participant in Part B, a 2-year OLE study. In Part B, participants will start at the dose of MYK-224 on which they completed Part A with the exception of those who have had a change in background HCM therapy. In instances where participants have had adjustments in background HCM therapy following their completion of Part A, they may either resume the background therapy upon which they completed Part A at least [REDACTED] prior to screening for Part B or start Part B at a 5-mg dose (see [Section 7.4](#)). After the initial [REDACTED] of Part B, clinic visits will occur every [REDACTED] and will include clinical evaluation of symptoms, AE/SAE assessment, ECGs, TTEs, PK sampling, [REDACTED], and laboratory assessments. Dose modifications during Part B will be guided by local site-read TTEs (See [Section 7.4.2](#) for details).

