7.1 Study Interventions Administered

The initial dose and timing of dose titration for each participant is described in [Section 5.1](#).

MYK-224 will be taken in a single oral daily dose, either administered at the investigation site or at home by the participant. Participants will take study drug as directed by the investigator/designee. Participants should be instructed to take the study drug at approximately the same time every day with approximately 8 ounces (240 mL) of water. If a participant forgets to take their daily dose at the usual time, they should take it as soon as they remember. Participants should never take more than 1 dose of study drug within an 8-hour period.

On study visit days, participants should fast for at least 4 hours prior to arrival at the clinical site and study drug dosing should be delayed until after study assessments are complete.

Table 7.1-1: Study Interventions

Cohort Name	Cohort 1 and Cohort 2
Intervention Name	MYK-224
Type	Drug
Dose Formulation	Tablet
Unit Dose Strength(s)	██████ mg
Dosage Level(s)	Once daily oral dose between 2.5 and 50 mg
Route of Administration	Oral
Use	Experimental
IMP and Non-IMP/AxMP	IMP
Sourcing	Provided centrally by the Sponsor
Packaging and Labeling	Study intervention will be provided in bottles. Each bottle will be labeled as required per country requirement.
Current/Former Name(s) or Alias(es)	MYK-224 BMS-986435

Abbreviations: AxMP, Auxiliary Medicinal Products; IMP, Investigational Medicinal Product.

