7.4.1.1 Dose Titration (Part A only)

All participants will receive a starting dose of 5-mg oral MYK-224. Dose titration will be based on the central read of each participant's TTE parameters collected 3 weeks (at least 21 days) after dose initiation during each dose titration cycle. [REDACTED]

[figure not shown]
[REDACTED], as outlined in [REDACTED]

Participants in Cohort 2 will follow the same titration scheme unless data from Cohort 1 or the ongoing CV029005 DDI study support an adjusted schedule.

In each participant, [REDACTED]

Once the target dose is reached, participants will proceed to the stable dosing period.

Left ventricular ejection fraction parameters for dose reductions as well as temporary and permanent dose discontinuation are also outlined in [REDACTED]. Both central and local TTE reads taken at any time may be used to guide these decisions as described in [Section 8.1.1.1](#) and [Section 8.1.2.1](#). In addition, a dose reduction to the last tolerated dose or dose interruption or discontinuation for safety may occur at any time during the dose titration period based on the clinical judgment of the investigator in consultation with the Medical Monitor. Following a dose reduction, participants will proceed to the stable dosing period and continue on the new dose for a minimum of 6 weeks.

█ [REDACTED]
█ [REDACTED]
█ [REDACTED]

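### As Section 10.4.3 states it, plasma concentrations are summarized without actual dose or titration cycle, so summaries after the first 5-mg cycle mix doses and tend to understate subgroup differences in exposure per mg

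*Combined protocol and SAP*

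**What the plan says.** The third secondary endpoint in Section 10.4.3 is "Summary of plasma concentrations", up to EOS-A. The analysis rule is one sentence: "All concentration-time data will be listed and summarized by timepoint and subgroup descriptively". The subgroups are the background-therapy groups of Section 5.2: monotherapy or beta-blocker in Cohort 1, nondihydropyridine calcium channel-blocker or disopyramide combination in Cohort 2.

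On dose, Section 7.4.1.1 says: "All participants will receive a starting dose of 5-mg oral MYK-224". Section 5.1.1.2 adds that this is "followed by up- or down-titration to doses between 2.5 mg and 50 mg", guided by each participant's own response. Under Table 2-2, the Week 3 echocardiogram informs the dose decision at Week 4, and footnote a has the four titration weeks repeated whenever the dose is adjusted. The Stable Dosing weeks in Table 2-3 also repeat.

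On purpose, the Section 4 objective is to assess PK in participants with symptomatic oHCM in Part A. The Protocol Summary says: "The results of this study are expected to facilitate future studies, including dose selection, in patient populations". Section 5.4 notes: "Both verapamil and diltiazem are moderate inhibitors of CYP3A4". It names CV029005, in healthy participants, as the drug-interaction study.

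**The concern.** A concentration summary is useful when the reader knows which dose produced it. Here the two stated classifiers, timepoint and subgroup, fix the dose only during the first cycle. Later, a mean and SD for a cell blend pharmacokinetic variation with the spread of doses assigned.

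There is also a direction to the distortion. Dose is not assigned independently of exposure: a participant who reaches response sooner because of higher exposure per mg stops at a lower dose. Subgroups that differ in exposure per mg are therefore drawn towards similar concentrations. Similar EOT-A means could be misread as evidence that background therapy does not alter exposure in patients, and a later study choosing doses would have no tabulated exposure by dose above the starting level.

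**Working it through.** The plan gives no sample size, precision or power figure for the PK summary, so there is none to reproduce.

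**1. Permitted spread.** Section 7.1 gives "Once daily oral dose between 2.5 and 50 mg": 50 / 2.5 = 20-fold. This is what is allowed; the spread that will occur is unknown.

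**2. What each cell contains.**

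| Samples | Dose within a subgroup cell |
|---|---|
| Day 1A; first-cycle Titration Weeks 1 and 3 | 5 mg for all, barring an early safety reduction |
| Titration Weeks 1 and 3, second cycle on | mixed |
| Titration Week 3 with cycles not separated | mixed; participants contribute unequal numbers of samples |
| Stable Dosing and EOT-A | mixed |

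**3. Why titration pulls subgroups together.** Write concentration as C = k × D, where k is exposure per mg and D is dose (linear PK, assumed). Suppose titration stops once C reaches 20 arbitrary units.

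- Subgroup 1, k = 1: stops at 20 mg, C = 20.
- Subgroup 2, k = 2: stops at 10 mg, C = 20.
- Raw EOT-A ratio: 20 / 20 = 1.00.
- Per-mg ratio: (20 / 10) / (20 / 20) = 2.00.
- Ratio at the common 5 mg: 10 / 5 = 2.00.

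**4. With variability.** Two simulations used this stopping rule with a 50-mg cap. None of their PK inputs is in the documents.

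- Simulation 1: between-participant CV 35% for k and 50% for the effective concentration; 5-mg steps; median effective level 10, 20 or 30 units at 1 unit per mg.
- Simulation 2: CV 40% for k; three dose grids.

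Subgroup ratios of geometric means for a true 2-fold difference in k:

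| Summary | Ratio |
|---|---|
| First cycle, all at 5 mg | 2.00 |
| Raw EOT-A, simulation 1 | 1.13 to 1.18 |
| Raw EOT-A, simulation 2 | 1.06 to 1.15 |
| Titration Week 3 pooled over cycles | 1.35 to 1.43 |
| Dose-normalized EOT-A | 2.00 |

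On the log scale, raw EOT-A keeps between ln 1.06 / ln 2 = 0.08 and ln 1.18 / ln 2 = 0.24 of the difference. Pooling Week 3 over cycles keeps ln 1.35 / ln 2 = 0.43 to ln 1.43 / ln 2 = 0.52. In simulation 2, true ratios of 1.5 and 3 appear as 1.03 to 1.09 and 1.12 to 1.25 at EOT-A. The dose-normalized 2.00 is a consequence of assuming linearity, not a finding.

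**5. Precision of the common-dose comparison.** With log-scale SD s = √ln(1 + 0.40²) = 0.385 and n per subgroup, the 90% CI is the observed ratio divided and multiplied by exp(t × s × √(2/n)), where t is the 95th percentile with 2n − 2 degrees of freedom. Subgroup size is redacted, so n is assumed: 5 gives 1.57, 8 gives 1.40, 10 gives 1.35. The comparison is descriptive.

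**The case against.** A reader might infer that the planned table would show little or no interaction anywhere, or no exposure at any dose. The documents do not support that. First-cycle samples are taken at one common dose, and a by-timepoint, by-subgroup table can show the full ratio there. What is missing is any statement that cycles are kept apart when the week labels repeat, so that comparison is available but not secured.

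A reader might also infer that the PK endpoint exists to measure the CYP3A4 interaction. It does not: the objective names no interaction, Section 5.4 assigns that question to CV029005, and Cohort 1 excludes the inhibiting calcium channel-blockers. That stands. CV029005 is in healthy participants, however, and the objective here is PK in oHCM.

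Concentrations are also listed and enter the PK/PD regression, which uses concentration whatever the dose. That is useful for dose selection, but it relates concentration to response, not dose to concentration, and a listing is not a summary. The SAP is to add technical detail (Section 10.4) and is not in the public document; the PK sampling tables and exploratory endpoints are redacted or not shown. A by-dose summary may exist there, so the point is limited to what 10.4.3 states.

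Finally, the simulated ratios depend on their inputs. The trial titrates on echocardiography, not on a concentration. The simulations gave subgroups the same effective-concentration distribution, yet Table 3.3.1-1 describes the background drugs as negative inotropes, so the concentrations needed may differ. That weakens the size quoted; it also makes a raw EOT-A contrast harder to read as pharmacokinetic.

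**Conclusion.** The concern holds in a limited form. As 10.4.3 is written, concentration summaries from the second cycle on, and at Stable Dosing and EOT-A visits, can mix doses within a 20-fold permitted range. They do not give exposure at any dose and will tend to understate subgroup differences in exposure per mg. The mixing follows from the text alone, and the direction from titration to response. The size, roughly 1.1 to 1.2-fold at EOT-A for a true 2-fold difference, is illustrative and rests on assumed linear PK, variability, dose steps and a shared effective-concentration distribution.

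First-cycle results are unaffected if cycles are kept separate. No hypothesis test or primary endpoint is touched. The change is worth making because it is cheap and improves what the study can say about PK in oHCM.

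**What to change.** In Section 10.4.3 and the SAP:

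1. Index PK timepoints by titration cycle as well as week.
2. Summarize predose concentrations by actual dose at sampling and subgroup. This needs no linearity assumption.
3. Add dose-normalized geometric means with CV by subgroup, stating the dose-linearity assumption.
4. Present the Cycle 1 Week 3 predose concentration as the descriptive between-subgroup comparison at a common dose, provided the cohorts share the same starting dose; Section 5.4 allows Cohort 2's regimen to change.

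No new samples are needed: Section 7.6 already records dosing, and Section 9.5.1 requires actual sample times. The cost is wording and a few more tables. Cells at the higher doses will be small, and some may be better left to the listing.

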10.4.4 Exploratory Endpoint(s)

Table 10.4.4-1: Endpoints

[figure not shown]

Table 10.4.4-1: Endpoints

[figure not shown]

Table 10.4.4-1: Endpoints

[figure not shown]
[figure not shown]

Table 10.4.4-1: Endpoints

10.4.5 Other Safety Analysis

Not applicable.

10.4.6 Other Analyses

Not applicable.

12 APPENDICES

APPENDIX 1 ABBREVIATIONS AND TRADEMARKS

Term	Definition
A	late diastolic mitral inflow velocity
ACC	American College of Cardiology
ACCF	American College of Cardiology Foundation
ADA	anti-drug antibodies
[REDACTED]	[REDACTED]
AED	automated external defibrillator
AE	adverse event(s)
AESI	adverse event(s) of special interest
AHA	American Heart Association
ALP	alkaline phosphatase
ALT	alanine aminotransaminase
[REDACTED]	[REDACTED]
AR	additional research
ASA	alcohol septal ablation
AST	aspartate transaminase
AT	ALT (alanine aminotransaminase) or AST (aspartate transaminase)
[REDACTED]	[REDACTED]
[REDACTED]	[REDACTED]
[REDACTED]	[REDACTED]
AxMP	Auxiliary Medicinal Product
BICR	Blinded Independent Central Review
BMI	body mass index
BMS	Bristol-Myers Squibb Company
BP	blood pressure
CABG	coronary artery bypass grafting
CIOMS	Council for International Organizations of Medical Sciences
[REDACTED]	[REDACTED]
CNS	central nervous system
[REDACTED]	[REDACTED]
CONSORT	Consolidated Standards of Reporting Trials
COVID-19	coronavirus disease 2019

Term	Definition
CRF	case report form
CRO	contract research organization
CSR	Clinical Study Report
CTAg	clinical trial agreement
CTR	cardiothoracic ratio
Ctrough	trough observed plasma or serum concentration
CV	cardiovascular
CYP3A4	cytochrome P-450 3A family isozyme 4
DBL	database lock
DDI	drug-to-drug interaction
DILI	drug-induced liver injury
DMC	Data Monitoring Committee
DNA	deoxyribonucleic acid
DSM	Diagnostic and Statistical Manual of Mental Disorders
DSUR	Development Safety Update Report
E	early diastolic mitral inflow velocity
e'	early diastolic mitral annular tissue velocity (note there is a lateral, septal and average of this parameter)
E/A	early to late diastolic mitral inflow velocity ratio (or early diastolic mitral inflow velocity to late diastolic mitral inflow velocity ratio)
E/e'	early diastolic mitral inflow velocity to early diastolic mitral annular tissue velocity ratio (note: there is a lateral, septal and average of this parameter, depending on where the tissue velocity assessment is made lateral or septal [medial annulus])
ECG	electrocardiogram
eCRF	electronic case report form
EDC	electronic data capture
EF	ejection fraction
eGFR	estimate glomerular filtration rate
EOS	end of study
EOS-A	end of study for Part A

Term	Definition
EOS-B	end of study for Part B
EOT	end of treatment
EOT-A	end of treatment for Part A
EOT-B	end of treatment for Part B
ESC	European Society of Cardiology
ET	early termination
ET-A	early termination for Part A
ET-B	early termination for Part B
EudraCT	European Clinical Trials Database
FDA	Food and Drug Administration
FIH	first-in-human
FPFV	first patient first visit
FS	Fractional Shortening
FSH	follicle-stimulating hormone
GCP	Good Clinical Practice
GLP	Good Laboratory Practices
GLS	global longitudinal strain
████	████████████████
HBV	hepatitis B virus
HCG	human chorionic gonadotropin
HCM	hypertrophic cardiomyopathy
HCV	hepatitis c virus
HF	heart failure
HIPAA	Health Insurance Portability and Accountability Act
HIV	human immunodeficiency virus
HIV RNA	human immunodeficiency virus ribonucleic acid
HOCM	obstructive HCM
hr	hour
HR	heart rate
HRT	hormone replacement therapy
████	██
████	██
HV	healthy volunteer

Term	Definition
I/E	inclusion/exclusion
IB	Investigators Brochure
IC50	half-maximal inhibitory concentration
ICD	implantable cardioverter defibrillator
ICF	Informed Consent
ICH	International Council on Harmonisation
IEC	Independent Ethics Committee
IMP	Investigational Medicinal Product
INR	International normalized ratio
IP/IMP	investigational [medicinal] product
IRB	Institutional Review Board
IRT	Interactive Response Technology
ITT	intention to treat
IUD	intrauterine device
IUS	intrauterine hormone-releasing system
IV	intravenous
KCCQ-23	Kansas City Cardiomyopathy Questionnaire (23-item version)
LV	left ventricular
LVEF	left ventricular ejection fraction
LVOT	left ventricular outflow tract
MACE	major adverse cardiovascular event
MAD	multiple ascending doses
MH	medical history
mm Hg	millimeters of mercury
MR	mitral regurgitation
██████████	██
MRI	magnetic resonance imaging
NA	not applicable
NASH	nonalcoholic steatohepatitis
NOAEL	no-observed-adverse-effect-level
██████████	██
NYHA	New York Heart Association
nHCM	non-obstructive hypertrophic cardiomyopathy

Term	Definition
oHCM	obstructive hypertrophic cardiomyopathy
OLE	open-label extension
OSS	overall summary score
PCI	percutaneous coronary interventions
PCR	polymerase chain reaction
PD	pharmacodynamics
PE	physical examination
PI	principal investigator
PK	pharmacokinetics
PL	physical limitation
PRO	patient-reported outcome
QD	once daily
QoL	quality of life
QRS	the interval between the beginning of the Q wave and the end of S wave in the electrocardiogram
QTc	QT interval corrected for heart rate
QTcF	QT interval corrected using Fridericia's method
R&D	research and development
RNA	ribonucleic acid
RR	respiratory rate
SAE	serious adverse event(s)
SAD	single ascending dose
SAP	statistical analysis plan
SARS-CoV-2	severe acute respiratory syndrome coronavirus 2
SCD	sudden cardiac death
SD	standard deviation
SOC	standard of care
SRT	septal reduction therapy
SUSAR	suspected unexpected serious adverse reaction
TB	tuberculosis
TBD	to be determined
TBL	total bilirubin level
Tmax	time at which maximum concentration (Cmax) occurs

Term	Definition
TTE	transthoracic echocardiogram
ULN	upper limit of normal
US	United States
USA	United States of America
UTN	universal trial number
vs	versus
WHO	World Health Organization
Wk	week
WNOCBP	women not of childbearing potential
WOCBP	women of childbearing potential
WS	Worldwide Patient Safety

